#### Primary questions:

- Do physicians administering InductOs understand the potential for heterotopic ossification occurrence after spinal interbody fusion?
- Do physicians administering InductOs know the appropriate measures to be taken to minimize the risk of heterotopic ossification occurrence?

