## 9. Research methods

#### 9.1 Study design

This study is a cross-sectional cohort analysis of InductOs-using spine surgeons to establish:

• their current level of knowledge regarding heterotopic ossification,

 the current level of knowledge, and degree of access to or utilisation of educational materials about the potential for post-surgical heterotopic ossification and practical risk minimisation measures.

A cross-sectional cohort study methodology was judged to be appropriate to meet the expectations of the European Medicines Agency (EMA) based on:

- The nature of the medicinal product: single use implantation in a relatively small target population
- The nature of heterotopic ossification which is not an uncommon adverse event of many orthopaedic procedures and it does not always manifest clinically
- The lack of appropriate data fields captured in the national spine registries across Europe,
- The period over which the educational materials have been available (since summer 2017)

The cohort study will be composed of an anonymous, online survey (see Annex 3) with the aim of answering the study questions outlined in section 8.

The screening for eligibility and online interviews will be conducted in the surgeon's native language. All materials will be prepared using the English master questionnaire as the baseline (see Annex 3). Translations will undergo appropriate quality checks prior to sign off by the research team.

The researchers will secure responses from 55 individuals from the four selected countries split proportionally based on usage, see section 9.5.

A pilot project of 2 surgeons will test the survey for clarity and accuracy of response and translated materials in an iterative manner. If no changes are made, then the pilot recruits will be included in the main cohort.

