## 9.7 Data analysis

The study population will include all physicians who are screened, are eligible for this study, and completed the questionnaire. All statistical summaries in this study will be descriptive. Frequencies and percentages, with 95 % confidence intervals (CIs) where appropriate, will be presented. Country specific data will be presented. Additional exploratory analyses and sensitivity analyses may be conducted to identify difference between groups of responders.

The primary analysis is aimed at evaluating the proportion of physicians that is aware of the risk of heterotopic ossification and measures described in the educational materials to minimize that risk. A respondent is considered to be aware if they answer 75 % of the questions with regards to heterotopic ossification and the applicable minimization measures correctly. In the questionnaire there are 12 (sub)questions raised on the occurrence of heterotopic ossification and the related risk minimization measures. Hence a surgeon needs to answer 9 of these correct to be considered aware. In Annex 3 the (sub)questions included in the scoring of awareness are marked. The aRMM will be considered effective if 80 % of the respondents are aware of the described risk of heterotopic ossification and the appropriate measures to minimize them. With the targeted 55 respondents, this means 44 or more need to be aware.

The secondary analysis is aimed at identifying the source of physician knowledge. Based on the received data it will be determined to what extent the educational materials are used and are considered an important source of information for the respondents.

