11-	Retrograde ejaculation	Y / N
12-	Others, please specify	Y / N

As the terms ectopic and heterotopic ossification are used interchangeably in some publications, we will use heterotopic ossification to describe both concepts. Heterotopic

ossification is one of the known adverse reactions to InductOs. Can you please indicate for each of the following statements whether it is true or false?

1	Heterotopic ossification can occur during lumbar arthrodesis	True / False
2	Heterotopic ossification occurs with and without the use of InductOs	True / False
3	Heterotopic ossification forms quickly	True / False
4	Heterotopic ossification can lead to nerve compression	True / False
5	Radicular pain is never the result of heterotopic ossification	True / False
6	Heterotopic ossification can occur asymptomatic	True / False
7	Heterotopic ossification occurs more often in patients undergoing a surgery with an anterior approach than in surgery with a posterior approach.	True / False

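### Two true/false statements in Annex 3 are loose about the timing of heterotopic ossification: one has no time frame at all, the other says during surgery where the objective says after it

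*Protocol*

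**What the plan says.** The primary question in protocol section 8 is "Do physicians administering InductOs understand the potential for heterotopic ossification occurrence after spinal interbody fusion". Section 9.1 likewise speaks of knowledge "about the potential for post-surgical heterotopic ossification and practical risk minimisation measures". Both place the event after the operation.

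The questionnaire in Annex 3 has a block of seven statements on heterotopic ossification. The surgeon is to indicate for "each of the following statements whether it is true or false"; no don't-know option is shown. Statement 1 is "Heterotopic ossification can occur during lumbar arthrodesis" and statement 3 is "Heterotopic ossification forms quickly".

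Section 9.7 builds the primary endpoint from such items: "In the questionnaire there are 12 (sub)questions raised on the occurrence of heterotopic ossification and the related risk minimization measures". A surgeon with at least 9 of the 12 correct counts as aware. The measures count as effective if 80 % of respondents are aware, which is 44 of the targeted 55. Annex 3 marks the scored items and the correct answers by text colour.

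**The concern.** A knowledge item should be answered by what the respondent knows, not by how the sentence is read.

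- **Statement 1** uses a different time reference from the objective it serves. Read as *in the setting of* the procedure, it is true. Read as *while the operation is under way*, a surgeon who thinks of the event as post-surgical, as section 9.1 does, can answer False.
- **Statement 3** gives no unit, starting point or comparator for the speed of formation, and nothing else in the protocol supplies one. Two surgeons with the same knowledge can answer differently because one thinks in days and the other in months. A scoring key fixes which answer earns the point; it does not make the sentence determinate.

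The pass mark leaves room for three errors in 12. If both items are scored, they can use up two of those three for reasons unrelated to awareness. They can also give points to surgeons who do not know the answer. Either way, noise enters the proportion that is compared with 80 %.

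**Working it through.** **Wording, side by side**

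| Place | Time reference | Procedure |
|---|---|---|
| Primary question, section 8 | after | spinal interbody fusion |
| Section 9.1 | post-surgical | not specified |
| Annex 3, statement 1 | during | lumbar arthrodesis |
| Annex 3, statement 3 | quickly, undefined | none |

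**The plan's own cut-offs.** 0.75 × 12 = 9 and 0.80 × 55 = 44. Both agree with section 9.7.

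**Are the two statements scored?** The colours are not visible in the text at hand (not a fault of the plan), so this is inference. One count gives exactly 12: the heterotopic ossification line in the adverse-reaction list (1), the seven statements (7), and the filling, placement, barrier and irrigation/drain questions (4). But the irrigation/drain question also asks for true or false on each of four lines. Counted as four, the implantation items number 1 + 1 + 1 + 4 = 7. That leaves 5 scored items among the other eight, so at least three of those eight would be unscored. The former count is the simpler one; neither is proved.

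**Size, if they are scored.** The documents give no item-level rates, so the following are assumptions: items are independent, each clear item is answered correctly with probability q, and an unclear item is answered correctly with probability 0.5. Write B(n, k) for the probability of at least k correct among n clear items.

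- All clear: B(12, 9).
- One at chance: 0.5 × B(11, 8) + 0.5 × B(11, 9).
- Two at chance: 0.25 × B(10, 7) + 0.5 × B(10, 8) + 0.25 × B(10, 9).

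At q = 0.85:

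- All clear: 0.908.
- One at chance: 0.5 × 0.9306 + 0.5 × 0.7788 = 0.855.
- Two at chance: 0.25 × 0.9500 + 0.5 × 0.8202 + 0.25 × 0.5443 = 0.784.

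| q | All clear | One at chance | Both at chance |
|---|---|---|---|
| 0.80 | 79.5 % | 72.8 % | 65.3 % |
| 0.85 | 90.8 % | 85.5 % | 78.4 % |
| 0.90 | 97.4 % | 94.6 % | 89.6 % |
| 0.95 | 99.8 % | 99.2 % | 97.2 % |

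**At the protocol's planning value.** Section 9.5 expects 90 % awareness. B(12, 9) = 0.90 at q = 0.846. With one item at chance, awareness is 84.5 % and the probability of at least 44 aware of 55 falls from 0.99 to 0.87. With both at chance, the figures are 77.3 % and 0.39.

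**Milder ambiguity.** At q = 0.85 with both items answered correctly 70 % of the time, awareness is 85.9 % and the probability of at least 44 of 55 is 0.92.

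**Where the 80 % line is crossed.** All-clear awareness reaches 80 % at q = 0.802. With one item at chance it needs q = 0.827, and with both q = 0.857. So the wording alone moves expected awareness across 80 % only for q between 0.802 and 0.827 (one item) or 0.802 and 0.857 (both).

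**The case against.** The other side has a good case on statement 1. The lead-in to the block tells the surgeon that heterotopic ossification is a known adverse reaction to the product. The adverse-reaction question before it already uses the same preposition, during, for the treatment setting. After that, a statement that something *can* occur points to True, and a 50 % correct rate is implausible. This stands: statement 1 is a mismatch with the objective rather than a trap, and the scenario with both items at chance is a worst case.

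On statement 3, the educational materials repeat the SmPC, and neither is available here. If they describe the speed of formation in the same word, surgeons who have read them have a reference. That cannot be checked, and the protocol itself supplies none.

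Section 9.1 also plans translation quality checks and an iterative pilot that tests clarity. This helps, but the pilot has two surgeons for a four-country survey, and the wording can be put right before it starts.

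A reader might infer more than this:

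- *The endpoint no longer measures the primary question.* At most two of 12 items are affected, three errors are tolerated, and scoring of the two items is unconfirmed.
- *The bias runs only against aware surgeons.* An item answered by reading rather than knowledge also credits surgeons who do not know.
- *The broader word arthrodesis is a second error.* If the event can occur with interbody fusion, it can occur with the wider class, so the answer does not change.
- *Translation will fix the wrong sense, differently by country.* No translation is in the documents, so this is conjecture.

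**Conclusion.** The point holds as a wording fault of modest size. Statement 3 is indeterminate as written. Statement 1 departs from the time reference of the primary question and of section 9.1, although True is its likely reading.

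The effect on the primary endpoint is conditional on the items being scored, which is likely but not verifiable from the text at hand. Under independence and 0.85 per item, the probable case (only statement 3 at chance) lowers awareness from 91 % to about 85 %, still above the criterion. Only with both at chance does it fall to 78 %, below 80 %. Near the protocol's expected 90 % awareness the picture is the same. At 0.90 per item or more, even the worst case stays above 80 %; at 0.80, the criterion is missed with clear items as well.

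The documents do not support saying that the study will wrongly fail. They do support saying that two items can add avoidable error to its main result.

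**What to change.** Before translation and pilot:

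1. Reword statement 1 to match the primary question, for example *Heterotopic ossification can occur after lumbar interbody fusion*.
2. Give statement 3 the time frame or comparator used in the SmPC and educational materials, if they contain one.
3. If they do not, take statement 3 out of the score, preferably replacing it with another scored item so that 9 of 12 stands. If it is scored now and is not replaced, restate the denominator and pass mark in section 9.7. Since 0.75 × 11 = 8.25, 9 of 11 would be needed. That is stricter than 9 of 12: at 0.85 per item, awareness would be 77.9 % against 90.8 %. A mark of 8 of 11 is 72.7 %, below the stated 75 %.
4. Ask the pilot surgeons specifically whether each of the two statements has a single reading in the language they test.

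The cost is two sentences in the English master, with no added burden on respondents. After data collection the fault cannot be repaired; the items could only be left out of the score after the fact.

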# 7. Rationale and background

The active ingredient of InductOs is dibotermin alfa or recombinant human Bone Morphogenetic Protein 2. Its osteoinductive properties result in the induction of new bone tissue at the site of implantation.

InductOs is approved for:

- single-level lumbar interbody spine fusion as a substitute for autogenous bone graft in adults with degenerative disc disease who have had at least 6 months of non-operative treatment for this condition.
- treatment of acute tibia fractures in adults, as an adjunct to standard care using open fracture reduction and intramedullary unreamed nail fixation.

Instructions for proper preparation and administration of dibotermin alfa/ACS are provided in the Summary of Product Characteristics (SmPC) and instructions for reconstitution are provided in the labelling of the pack. The aforementioned instructions consist of routine measures to minimise important identified (heterotopic ossification, osteolysis/resorption bone increased, fluid collection) and potential risks (medication errors and incorrect use, malignancies, antibody formation) by providing information on the measures to take during administration of dibotermin alfa/ACS or situations to avoid.

Additional risk minimisation measures (aRMM) to increase awareness about the identified risk of heterotopic ossification (especially in posterior surgical approaches for lumbar interbody fusion) and the potential risk of medication errors and misuse are available in the form of educational materials. These educational materials also aim at providing guidance on how to manage these risks. The aRMM present the information from the Summary of

Product Characteristics (SmPC) supported with visual aids, e.g. a demonstration of the correct preparation technique. The aRMM and related educational materials contain no information which is not contained in the SmPC.

InductOs educational materials consist of a preparation guide, two videos (one for each indication), and the SmPC. The educational materials can be accessed through a dedicated website, or upon request to the MAH.

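### The only item that compares surgical approaches (true/false statement 7) gives the same answer for the posterior-risk message and for a belief in no difference, so it cannot show that the message was received

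*Protocol*

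**What the plan says.** Sections 4.2 and 7 of the protocol describe the additional risk minimisation measures as raising awareness of heterotopic ossification, "especially in posterior surgical approaches for lumbar interbody fusion".

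In Annex 3 (Questionnaire on InductOs), respondents are asked to indicate for "each of the following statements whether it is true or false". There is no third option. Statement 7 reads: "Heterotopic ossification occurs more often in patients undergoing a surgery with an anterior approach than in surgery with a posterior approach".

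Section 9.7 sets the scoring. "In the questionnaire there are 12 (sub)questions raised on the occurrence of heterotopic ossification and the related risk minimization measures", and "Hence a surgeon needs to answer 9 of these correct to be considered aware". The measures count as effective at 80 % awareness: "With the targeted 55 respondents, this means 44 or more need to be aware". Annex 3 marks the scored items and the correct answers by text colour, which is lost in the text available here.

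**The concern.** A surgeon may hold one of three beliefs about approach: risk is higher with anterior surgery, equal, or higher with posterior surgery. A two-option statement must merge two of them. Statement 7 asserts the anterior direction, so it merges equal with posterior-higher: both lead to False. Section 7 stresses the posterior approach, and the surgeon who has not taken that in but sees no difference gets the same credit as the one who has.

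What is at stake is the content validity of one item and, through it, the awareness score. The success rule in section 9.7 compares the observed count with 44 of 55 and leaves no margin, so a mark that can be earned without the knowledge favours a finding that the measures are effective.

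**Working it through.** **The plan's own figures.** 0.75 × 12 = 9 and 0.80 × 55 = 44. Both reproduce.

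**Does another item cover the message?** Going through Annex 3:
- Statements 1 to 6, the adverse-reaction list, the filling question and the irrigation and drain question do not mention approach.
- The two questions set in a PLIF ask where the matrix may go and what applies to a physical barrier. They test technique within a posterior procedure, not relative risk by approach.
- The question on the percentage of time per approach describes practice and has no right answer.

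Statement 7 is therefore the only comparison of approaches.

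**Answer by belief.**

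| Belief | Reply to statement 7 | Mark if keyed False | Mark on a three-option item |
|---|---|---|---|
| Anterior higher | True | 0 | 0 |
| No difference | False | 1 | 0 |
| Posterior higher | False | 1 | 1 |

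The two scorings differ only in the middle row. For surgeons who answer as they believe, the present wording can raise the score and never lower it.

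**Is it scored?** One natural count is 1 adverse-reaction option + 7 statements + 4 questions on measures (filling, placement, barrier, irrigation and drain) = 12, which includes statement 7. It is not the only count. If the four irrigation and drain lines are scored separately, then 1 + 1 + 1 + 1 + 4 + 4 statements = 12 as well, and statement 7 could be left out.

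**Size if it is scored.** Assumptions, none from the documents: the other 11 items are independent with a common probability p of a correct answer; a share s of surgeons believe in no difference; the rest hold the posterior belief.

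The mark is decisive when exactly 8 of the other 11 are right: P = 165 × p⁸ × (1 − p)³. The overstatement is s × P. Awareness as now worded is P(at least 8 of 11). With the mark withheld from the share s, it is that value minus s × P. The last column is the binomial probability of at least 44 of 55. With s = 20 %:

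| p | Decisive share P | Overstatement | Awareness now → withheld | P(≥ 44 of 55) now → withheld |
|---|---|---|---|---|
| 0.75 | 25.8 % | 5.2 points | 71.3 % → 66.2 % | 0.10 → 0.02 |
| 0.80 | 22.1 % | 4.4 points | 83.9 % → 79.5 % | 0.83 → 0.54 |
| 0.85 | 15.2 % | 3.0 points | 93.1 % → 90.0 % | 1.00 → 0.99 |
| 0.90 | 7.1 % | 1.4 points | 98.1 % → 96.7 % | 1.00 → 1.00 |

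At p = 0.80 the last figure is 0.70 for s = 10 % and 0.38 for s = 30 %, against 0.83 as now worded.

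**The case against.** The strongest reply has four parts.

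1. Whether statement 7 is scored, and keyed False, cannot be read here. This stands: both are inferences, from the count of 12 and from sections 4.2 and 7. If the item is not scored, there is no bias in the score, but then no scored item compares approaches at all.

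2. Sections 4.2 and 7 mention posterior approaches only in a parenthesis. They do not say that the materials state a comparative frequency, and the primary questions in section 8 do not mention approach. This also stands in part. The materials are not at hand, so the key should be checked against them. But the protocol chose to ask a comparative question, and the question should separate the answers it compares.

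3. Reverse wording is an accepted guard against agreement bias. That is right, and statements 5 and 7 appear to be the only reversed ones. It argues against simply swapping the two approaches in the statement: statement 5 would be left as apparently the only reversed one. It does not argue against a three-option item.

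4. The effect is small away from the threshold. Section 9.5 expects 90 % awareness, which in the model corresponds to p of about 0.85. There the overstatement is about 3 points and the verdict hardly changes.

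Two stronger readings are tempting. A reader might infer that the posterior message is never tested. That goes too far: the reversed belief does lose the mark, and the two PLIF questions examine measures in a posterior procedure. A reader might also infer that statement 7 is detached from InductOs and lumbar surgery. The context does not support that: the stem presents heterotopic ossification as a known reaction to InductOs, the preceding question concerns lumbar interbody fusion, and statement 1 names lumbar arthrodesis.

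**Conclusion.** The point holds as a weakness of item design. By its wording alone, statement 7 cannot distinguish a surgeon who knows that the posterior approach is the one stressed from one who sees no difference, and no other item makes up for it.

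The effect on the primary result is conditional. If the item is scored and keyed False, it is 1 of 12 marks and its bias runs upwards only. With an assumed 20 % no-difference share, the overstatement is about 5 points at p = 0.75 and 1.4 points at p = 0.90. The verdict on effectiveness is sensitive mainly when awareness is near 80 %. The documents give no basis for the belief share or for p, so they do not support a claim that the study's conclusion will be wrong. Nor is there an arithmetic error or a contradiction in the protocol here. This is a cheap improvement worth making before fielding.

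**What to change.** Replace statement 7 with one single-choice item asking whether, when InductOs is used in lumbar interbody fusion, heterotopic ossification occurs more often with an anterior approach, more often with a posterior approach, or with no difference between them. Score only the answer that fits sections 4.2 and 7, after checking it against the educational materials. If statement 7 is among the scored items, the count of 12 and the cut of 9 are unchanged.

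The cost is one reworded item in the English master, its retranslation, and its inclusion in the pilot that section 9.1 already plans. Measured awareness may come out slightly lower.

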## Pre-implantation

In the operating theatre InductOs is reconstituted and added to the collagen matrix. When filling the hollow geometry of the lumbar interbody fusion device, a surgeon needs to:

- (1) Loosely fill the lumbar interbody fusion device with the wetted matrix, while preventing compression of the matrix and overfilling of the volume intended for new bone formation
- (2) Firmly fill the lumbar interbody fusion device with the wetted matrix, while preventing compression of the matrix and overfilling of the volume intended for new bone formation.
- (3) Loosely fill the lumbar interbody fusion device with the wetted matrix, while allowing compression of the matrix and overfilling of the volume intended for new bone formation
- (4) Firmly fill the lumbar interbody fusion device with the wetted matrix, while allowing compression of the matrix and overfilling of the volume intended for new bone formation

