## 9.5 Study size

The minimum sample size needed to obtain a proportion with confidence interval with the lower limit above the 80 % minimum awareness was calculated. For this calculation an alfa of 0.05 with a two-sided interval and a distance from proportion to limit of 0.1 was used with the expected proportion of 90 %. This leads to a minimum sample size of 35.

To ensure inclusion of data from the different participating countries, this study aims at collecting responses from physicians covering roughly 10 % of purchasing pharmacies that have received InductOs in the past 2 years in each target country. However, if a greater number of respondents complete the questionnaires for a given target group, these responses will be integrated into the analyses.

The following number of completed surveys are planned per country:

France: 15Germany: 15

- United Kingdom: 15

- Ireland: 10

This brings the total to 55 completed surveys which is above the calculated minimum sample size. Taking into account response rate of roughly 60 % and screening failures an estimated 120 surgeons will be screened for eligibility.

Recruitment rate will be monitored by the researchers; and if it becomes apparent that the there is a risk of the study not meeting the recruitment target then other countries with InductOs sales will be included in the study to widen the pool of potential participants. In the selection of additional countries for recruitment, priority will be given to countries where the existing translated materials are used.

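### The only pre-implantation question has options whose wording points to one answer; if it counts among the 12 scored (sub)questions, it can bias awareness upward by a few points

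*Protocol*

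**What the plan says.** Annex 3 of the protocol, under Pre-implantation, holds a single question: how a surgeon fills the hollow of the interbody device. Its four options combine two verbs with two conditions:

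- Option 1: loosely, preventing compression and overfilling.
- Option 2 begins "Firmly fill the lumbar interbody fusion device with the wetted matrix, while preventing compression of the matrix and overfilling of the volume intended for new".
- Option 3 begins "Loosely fill the lumbar interbody fusion device with the wetted matrix, while allowing compression of the matrix and overfilling of the volume intended for new".
- Option 4: firmly, allowing compression and overfilling.

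Section 9.7 sets the score: "In the questionnaire there are 12 (sub)questions raised on the occurrence of heterotopic ossification and the related risk minimization measures". It continues: "Hence a surgeon needs to answer 9 of these correct to be considered aware". The risk minimisation measures are judged effective at 80 % of respondents aware, that is 44 of the targeted 55.

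Section 9.3 lists knowledge of safe use before implantation as a study variable. Section 9.10 counts non-leading questions among the safeguards against response bias. Section 9.8 randomises the answer options, and section 9.1 plans a pilot in two surgeons.

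**The concern.** A knowledge item works only if someone who does not know the instruction finds the wrong options believable. Here options 2 and 3 each join a verb to a condition that pulls against it, and options 3 and 4 have the surgeon permit something named as excess. Only option 1 carries neither fault. It can be reached from the wording alone, which sits badly with the assurance in section 9.10.

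The planned controls do not catch this. Shuffling the options leaves their wording intact. A two-surgeon pilot for clarity will tend to pass a cued item, because such an item looks clear and is answered as intended.

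Two things are at stake. Whatever the scoring, the whole pre-implantation part of the knowledge variable rests on this one question. If it is also scored, respondents who lack the knowledge can gain a mark towards the pass mark of 9, and that pass mark feeds a fixed threshold.

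**Working it through.** **The plan's own figures.** Section 9.5 states "For this calculation an alfa of 0.05 with a two-sided interval and a distance from proportion to limit of 0.1 was used". The awareness anticipated there is 90 %, and the section concludes: "This leads to a minimum sample size of 35". The Wald formula gives n = 1.96² × 0.9 × 0.1 / 0.1² = 34.57, rounded up to 35. From section 9.7, 0.75 × 12 = 9 and 0.80 × 55 = 44. All three reproduce.

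**Is the item scored?** Annex 3 shows scored items and correct answers by text colour only, which the text at hand does not carry. That is no fault of the plan. Counting can give 12 either way:

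- With the fill item: heterotopic ossification in the adverse-reaction list (1), true/false statements (7), and fill, placement, barrier and irrigation once each (4).
- Without it: the same adverse-reaction item (1), true/false statements (7), and the four irrigation and drain statements counted singly (4).

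**What the cue is worth.** A blind guess among four options succeeds with probability 1/4. Striking out the two self-conflicting options raises this to 1/2. It approaches 1 only if the respondent also rejects option 4 because it permits overfilling.

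**Effect on the score if the item is scored.** Assumptions, none of them in the protocol: the other 11 items are independent, each answered correctly with probability q; the fill item is answered correctly with probability g; the key is the option left standing. Let T(n, k, q) be the binomial probability of at least k correct out of n. Then

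P(aware) = g × T(11, 8, q) + (1 − g) × T(11, 9, q).

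At q = 0.80, T(11, 8) = 0.839 and T(11, 9) = 0.617. An ordinary item (g = 0.80) gives 0.80 × 0.839 + 0.20 × 0.617 = 0.795. A free mark (g = 1) gives 0.839. Over a range of q:

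| q | P(aware), ordinary item | P(aware), free mark | Gain (points) | P(at least 44 of 55), ordinary → free |
|---|---|---|---|---|
| 0.70 | 0.493 | 0.570 | 7.7 | 0.000 → 0.000 |
| 0.75 | 0.649 | 0.713 | 6.4 | 0.011 → 0.099 |
| 0.80 | 0.795 | 0.839 | 4.4 | 0.540 → 0.834 |
| 0.85 | 0.908 | 0.931 | 2.3 | 0.996 → 1.000 |
| 0.90 | 0.974 | 0.981 | 0.7 | 1.000 → 1.000 |

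**By true awareness.** Solving for the q that gives a stated awareness with an ordinary item, then making the mark free:

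- 70 % becomes 75.8 %; P(at least 44 of 55) goes from 0.067 to 0.293.
- 75 % becomes 80.1 %; 0.246 to 0.590.
- 80 % becomes 84.3 %; 0.580 to 0.857.
- At the planned 90 %, the probability is already 0.993 without any free mark.

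**Elimination only.** For a surgeon who does not know the item, moving g from 0.25 to 0.50 raises P(aware) from 0.520 to 0.584 at q = 0.75, and from 0.673 to 0.728 at q = 0.80.

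**The case against.** The strongest reply is that this is an item-writing remark whose effect on the result is unproven. Much of that reply is fair:

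- A reader might infer that the item is certainly one of the 12 marks. The documents at hand do not show that; the count works with and without it.
- A reader might infer that the mark is almost free. Logic alone gives a guess rate of 1/2, the same as for each true/false statement in the questionnaire. Option 4 is self-consistent, and option 3 is awkward rather than impossible. Going beyond 1/2 needs a judgement about how surgeons react to the word overfilling, and the protocol has no item-level data on that.
- A reader might infer that the phrase about the volume meant for new bone gives the answer away. It stands in all four options and not in the stem, so it cannot separate them.
- A reader might infer that the 80 % verdict is inflated. The table sets g to exactly 1, and surgeons who know the instruction gain nothing, so the gains are ceilings.
- The word overfilling may belong to the message being tested. The educational materials are not at hand, so that cannot be checked.

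What the reply leaves standing is the construction of the options. The conflict in options 2 and 3 and the self-declared fault in options 3 and 4 can be read directly in Annex 3, and neither shuffling nor the pilot removes them.

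**Conclusion.** The fill question is cued, contrary to the assurance in section 9.10, and it is a weak measure of the one pre-implantation topic in the survey. If it is scored and the key is the option that the wording leaves standing, its bias on the awareness proportion is upward and amounts to a few points: at most 7.7 at q = 0.70, 4.4 at q = 0.80 and 0.7 at q = 0.90, under independent items of equal difficulty and a wholly free mark. It can change the 44-of-55 verdict only when true awareness is near 80 %; at the planned 90 % it makes no practical difference. The documents do not support saying that the verdict is inflated, only that it could be affected under these conditions. No position is taken on which filling technique is right.

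**What to change.** Before the pilot, rewrite the four options so that each is internally coherent, plausible and neutrally worded. Key the answer to the educational materials and leave the instruction being tested unchanged. A blanket ban on the word overfilling is not needed and might remove the message itself.

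Keep it as one item. If it is scored, splitting it would give 13 scored items, and 0.75 × 13 = 9.75, so section 9.7 would need a new pass mark.

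If it is scored, also report the primary proportion with and without it, and fix the pass mark for the reduced score in advance. Since 0.75 × 11 = 8.25, neither 8 nor 9 of 11 equals 75 %, and the choice matters: at q = 0.80 they give 0.839 and 0.617. Show both. Anyone with 9 of 11 also has at least 9 of 12, and anyone with 9 of 12 has at least 8 of 11, so the two figures bracket the primary result. Add the percentage answering this item correctly.

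The cost is rewording and retranslating one question, and possibly a slightly lower awareness figure. Doing it before the pilot also avoids a later change that could exclude the two pilot surgeons from the main sample.
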